### 1.2 Purpose

Primarily, the purpose of this phase I/II clinical trial for patients living with cervical spinal cord injury (SCI) is to promote recovery of the paretic upper limb and improve functional independence by using non-invasive brain stimulation (tDCS) in combination with upper limb rehabilitation to recruit any and all residual spared neural resources.

Secondarily, the clinical trial will determine the safety and feasibility of pairing tDCS with rehabilitation in individuals with SCI.

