In accord with the proposed Aim 2, patients receiving tDCS during rehabilitation show greater gains in excitability of the brain and the residual descending pathways devoted to weak muscles. Although at baseline, patients show a greater number of excitable brain sites devoted to the stronger than the weaker muscles, in line with findings of injury-induced imbalances in excitability reported in earlier preclinical and clinical studies ( $t_7, 0.05 = 1.82, p = 0.05$ ) [20, 26-31], after tDCS, balance tends to become restored. The number of brain sites devoted to the stronger muscles tends to decrease ( $t_6, 0.05 = 1.07, p = 0.16$ ), whereas that devoted to the weaker muscles tends to increase after tDCS ( $t_6, 0.05 = 1.43, p = 0.1$ ) (fig. 4A, D). What is equally compelling is that such re-balancing is not witnessed after rehabilitation (without tDCS); instead, patients show further increase in the number of brain sites devoted to the strong muscles ( $t_4, 0.05 = 1.84, p = 0.07$ ). Therefore, the ratio of weak vs. strong muscle map in the motor cortices shows larger gains after tDCS than after rehabilitation, i.e., the ratio or the balance shifts in favor of the weak muscles ( $t_{10}, 0.05 = 1.92, p = 0.08$ ). Restoration of balance is associated positively with gains in strength of the weak muscles. Patients who show the greatest gain in the number of brain sites devoted to weak muscles also experience the greatest gains in strength of those muscles. Thus, tDCS helps re-balance or restore the excitability of surviving neural resources, plasticity that is functionally adaptive.

Regarding Aim 3 of the proposed study, patients receiving tDCS during rehabilitation experienced no serious adverse events. Further, these patients were not any more likely to guess which group they were in compared to patients who received sham tDCS ( $\chi^2 = 0.69; p = \text{N. S.}$ ). Thus, overall, the application of tDCS during rehabilitation is safe for individuals with SCI based on the findings of our pilot study. Our study also shows that it is feasible to test tDCS against a placebo condition in the proposed randomized, sham-controlled, double blind, phase I/II safety-efficacy clinical trial.

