## 5.1 Study Objective

The objective of the proposed trial is to extend the scope of our pilot study and conduct a phase I/II multi-site randomized controlled, double-blinded clinical trial to test the safety, feasibility, efficacy, and mechanisms of delivering tDCS with rehabilitation in SCI. At least forty-nine (up to 54) patients with chronic, incomplete (having sparing to muscles in the upper extremities below the level of injury) C1-C8 SCI will be enrolled across 4 sites: Cleveland Clinic (at least 21[up to 25] subjects), Kessler Foundation/Kessler Institute for Rehabilitation (14 subjects), Cleveland VA Medical Center (6 patients), and MetroHealth Hospital (8 patients). Patients will first complete a baseline control phase lasting 3 weeks, during which they will continue with their typical routine and activities (fig. 4). After the baseline control phase, they will be randomly assigned to either receive tDCS ( $n = 22$ ) or sham tDCS ( $n = 22$ ) during rehabilitation. Rehabilitation will be given for 2 hours/day, 5 days/week for 3 weeks. Rehabilitation will especially involve exercises for weak muscles innervated below the level of injury, such as triceps (C7). After the completion of the rehabilitation/intervention phase, patients will participate in a 3-month follow-up phase, during which they will be asked to continue with exercises prescribed as part of the home-exercise routine. Up to 42 age matched healthy control participants will also be enrolled to record ‘normal’ neural indices (15 at the Cleveland Clinic, 6 at Kessler Foundation, 6 at Cleveland VA, and up to 15 at MetroHealth Hospital).

[figure not shown]

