**Table 2: Sample Size Estimation based on Power Analysis**

	Outcomes/Metrics	Effect size (tDCS vs. Sham)	$\alpha$	80%	85%	90%	95%
Aim 1	UEMS (# Weak muscles showing clinically detectable improvement)	0.938	0.05	40	44	52	62
	$\Delta\%$ Nine Hole Peg Test	1.033	0.05	32	36	42	52
Aim 2	$\Delta\%$ Map Ratio (Weak map/Strong map)	1.192	0.05	26	30	34	40

estimate sample sizes, based on two sample t statistics compiled at  $\alpha = 0.05$  for 80% power (Table 2). For Aim 1, data concerning strength/power of muscles and dexterity (NHPT) was used since both of these metrics are components of the primary outcome for Aim 1 (GRASSP). Based on between-group comparison of the numbers of weak (C6-T1) muscles that achieved clinically detectable improvements on MRC ( $\geq 1$  full grade gain [63, 64]), we would require a total of 40 patients, and based on between-group comparison of % improvement on the NHPT (pegs per second), we would require 32 patients for achieving 80% power. This estimate would be sufficient for Aim 2 as well. For Aim 2, data concerning motor cortical map excitability was used, as this is the primary outcome for Aim 2. Based on between-group comparison of % change in map ratio (weak map/strong map), we would require 26 patients for achieving 80% power. Considering that there could be attrition of 10%, we expect to enroll 44 patients. A sample of 44 patients with 22 patients included in each SCI group would also be sufficient for study of Aim 3, which is designed to show that tDCS+-rehab is at least as safe and feasible (no greater attrition or probability of guessing the group) as rehabilitation given alone (sham+-rehab).

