Safeguards and procedures are in place to ensure GCP are followed. Specifically, on-call CRU nursing staff and trained study staff will continually monitor patient safety and health during each site visit. Every 1 hour or whenever it becomes necessary, vital monitoring will be performed by CRU nursing staff, where values including blood pressure, heart rate, oxygen saturation and respiratory rate will be collected. In case vital measurements are significantly abnormal or a serious AE occurs, hospital-wide medical emergency response team will be paged; on-call physician ([name] at the Cleveland Clinic; [name] at the Cleveland VA Medical Center; [name] at Kessler Foundation and Kessler Institute for Rehabilitation; [name] at MetroHealth Hospital) will be contacted and on-call CRU nurses will be reached as well. Depending on the type of emergency, SCI physicians and emergency response team will determine the next course of action. In addition, study staff will always record minor but noticeable changes in patient's state and vitals. All staff will be required to have completed the basic life support training before conducting procedures on the study.

To date, no AEs have occurred during the duration of our current SCI pilot study. This is likely since we use fairly strict inclusion and exclusion criteria. However, should an AE occur that could have been prevented, clinical coordinators, under the direction of PI/Co-I's, will update the patient screening process to identify what makes a patient susceptible to such an event. In addition, all patients currently participating in the clinical trial would be informed of the event and any subsequent changes to the consent form through a re-consenting process.

*Special precautions taken to ensure confidentiality during data compilation and data sharing across sites:* Raw data of neurophysiology and functional metrics shared between Cleveland Clinic, Cleveland VA Medical Center Kessler Foundation/Kessler Institute for Rehabilitation and MetroHealth Hospital will be de-identified and placed on locked drives and will not affect patient confidentiality. Since only a copy of de-identified data will be transported between sites, original data will still be available at each site in case the copy is damaged or destroyed in transport. Still, to ensure that data is completely de-identified and that privacy rules are being followed, we will take additional precautions.

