### **11.1 Risks associated with TMS**

Transcranial magnetic stimulation (TMS) has been used in a growing number of laboratories worldwide since 1984, and safety guidelines have been developed. In the present study, the investigators will use all recommended safety precautions for TMS. Although unlikely, given the low levels of stimulation applied in the present study, the following side effects are still possible:

- Headache: Subjects may have a headache following TMS. This is believed to be due to muscle tension. In the case of headache, subjects will be offered acetaminophen or aspirin, which in all prior cases of headaches induced by TMS have promptly resolved the discomfort. The risk of headache is estimated to be approximately 10%-25%.
- Hearing: TMS produces a loud clicking sound when a current is passed through the stimulation coil. This loud clicking can result in ringing in the ear and temporary shifts in the subject's ability to determine the pitch and loudness of sounds, if no protection is used. To prevent this possible side-effect, we will ask subjects to wear earplugs that block the noise of the TMS. Hearing damage is possible; one person is known to have suffered permanent hearing damage when the hearing protection fell out of the ear. Animal and human studies have shown that earplugs or headphones can effectively prevent the risk of hearing disturbance due to TMS.

There are also several rare side effects of TMS:

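### Section 5.2 calls 44 patients sufficient to show tDCS is no worse than sham on safety and feasibility, but nothing was calculated for Aim 3, and 22 per arm can exclude only very large excesses

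*Combined protocol and SAP*

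**What the plan says.** Section 5.2 takes 40 patients from the Aim 1 strength outcome (two-sample t test, effect size 0.938, alpha 0.05, 80% power) and notes that this also covers Aim 2, which needs 26. It then adds attrition: "Considering that there could be attrition of 10%, we expect to enroll 44 patients". The next sentence says that 22 per group "would also be sufficient for study of Aim 3, which is designed to show that tDCS+-rehab is at least as safe and feasible" as rehabilitation with sham, which it spells out as "no greater attrition or probability of guessing the group". Table 2 has rows for Aims 1 and 2 only.

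Hypothesis 3 (section 5.4) repeats the claim and adds adverse effects. Section 9.4 says that vital signs, attrition, adverse events such as tingling, itching and burning, and correct guessing will be compared between the groups. It names no test, interval, confidence level or margin. Section 1.2 makes this the trial's second purpose: "Secondarily, the clinical trial will determine the safety and feasibility of pairing tDCS with rehabilitation in individuals with SCI".

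Section 5.1 gives a larger enrolment, "At least forty-nine (up to 54) patients with chronic, incomplete", while still stating 22 per group for randomization.

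**The concern.** To show that one arm is no worse than another, a trial must exclude an excess larger than some tolerated amount. A sample sized to detect a large difference in a continuous outcome says nothing about how small an excess in a yes/no rate it can exclude. With no margin, reference rate or interval for Aim 3, the word sufficient has nothing behind it.

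What is at stake is how the secondary purpose is reported. Similar rates in two small arms could be presented as having shown equal safety and feasibility while the data still allowed a large excess. The pilot shows how such a reading arises: from 8 v 6 patients and a non-significant chi-square, section 4.1 reports that "these patients were not any more likely to guess which group they were in compared to patients who received sham tDCS".

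**Working it through.** **1. Where the 44 comes from.** Inputs (section 5.2, Table 2): d = 0.938, alpha 0.05, 80% power, two-sample t. A two-sided noncentral-t calculation gives 38 in total against the stated 40. All 12 cells of Table 2 reproduce within 2 patients; a one-sided test would give 30, not 40. Attrition: 40 × 1.10 = 44 (40 / 0.90 = 44.4, so 45 by division). The 44 is thus Aim 1 superiority plus 10%. It exceeds the 26 for Aim 2. No Aim 3 quantity enters.

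**2. What 22 per arm can exclude.** Assumptions: one yes/no outcome per patient; the same true rate p in both arms; success means that the upper limit of the two-sided 95% Newcombe interval for (tDCS − sham) lies below the margin m. With Wilson limits (l, u) for each arm,

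U = p1 − p2 + √[(u1 − p1)² + (p2 − l2)²],

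and the probability of success is the sum of Bin(x1; 22, p) × Bin(x2; 22, p) over all (x1, x2) with U < m, computed exactly.

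The attrition rate is the plan's 10%. The documents give no correct-guess rate; 50% is assumed, with 30% to 70% as the range.

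| Margin | 10 points | 20 points | 25 points | 28 points | 30 points | 40 points |
|---|---|---|---|---|---|---|
| p = 10% | 12.5% | 54.4% | 69.3% | 80.7% | – | – |
| p = 50% | 9.4% | 32.6% | – | – | 56.1% | 85.4% |

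Smallest margin excluded with at least 80% probability (searched in half-point steps):

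| Per arm, interval | p = 10% | p = 50% |
|---|---|---|
| 22, two-sided 95% | 28.0 | 39.5 |
| 24, two-sided 95% | 27.5 | 37.5 |
| 27, two-sided 95% | 25.0 | 35.0 |
| 22, one-sided 5% | 24.5 | 36.0 |

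At 22 per arm, a guess rate of 30% or 70% gives 36.5. If only completers are asked to guess (20 per arm, assumed), the 50% figure is 41. For rarer events at 22 per arm the margin is 22 points at 2% and 24 at 5%.

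**3. Other interval methods.** The closed form (1.960 + 0.842) × √[2p(1 − p)/n] gives 2.802 × √(0.18/22) = 25.3 points at 10% and 2.802 × √(0.50/22) = 42.2 points at 50%. Exact enumeration gives 28.1 and 40.7 with Miettinen-Nurminen, and 26.2 and 40.3 with Agresti-Caffo.

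**4. Best single results.** With no events in either arm (0/22 v 0/22), the Newcombe upper limit is z²/(n + z²) = 3.84/25.84 = 14.9 points (12.5 at 27 per arm). For 2/22 v 2/22 it is 19.8; for 11/22 v 11/22 it is 27.3.

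**5. If non-significance were read as no worse.** The documents do not state this rule, so these figures are conditional. With 22 per arm and a two-sided 5% test, the power to detect 20% v 10% is 15.2% (uncorrected chi-square) or 8.5% (Fisher), so a doubling of attrition would be missed 84.8% to 91.5% of the time. For guessing at 70% v 50% the power is 26.4% or 17.5%, so the miss rate is 73.6% to 82.5%.

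**6. Adverse-event figures in the documents.** Section 9.6 says "To date, no AEs have occurred during the duration of our current SCI pilot study"; section 4.1 is narrower, reporting no serious events in tDCS patients. Section 11.1 gives a rate for TMS, which both arms receive: "The risk of headache is estimated to be approximately 10%-25" per cent. Neither is a planning rate for the symptoms that section 9.4 will compare. Even if the pilot's zero covers all 14 patients (assumed), its one-sided 95% upper limit is 1 − 0.05^(1/14) = 19.3%.

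**The case against.** The strongest reply is that this is a phase I/II trial which does not claim formal power for safety. Section 9.4 speaks of comparing and anticipating, section 5.1 of recording, and no section commits to treating a non-significant test as proof. On that reading Aim 3 is descriptive and one loose sentence has little consequence. Part of this stands: no stated number is wrong, and the miss rates in step 5 are only conditional. But section 5.2 says Aim 3 is designed to show the result, and section 5.4 makes it a hypothesis. If the aim is descriptive, the sufficiency sentence should go.

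A second reply is that the criterion (80% probability, two-sided 95%), the 50% guess rate and 22 per arm are choices that widen the margins. The 50% rate is indeed close to the worst case, and section 5.1 now enrols more than 44. The alternatives above still leave about 24 to 28 points for attrition and about 35 to 42 for guessing, so the conclusion does not depend on these choices.

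A third reply is that removing one sentence would cure the unsupported claim, and recasting Hypothesis 3 goes further. That is fair. The recast is advisable because sections 5.4 and 9.4 carry the same expectation without a margin.

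**Conclusion.** The concern holds. The statement that 44 patients suffice for Aim 3 has no calculation behind it, and the design supports it only for very wide margins: about 28 points for attrition at 10% and about 40 points for correct guessing at an assumed 50% (22 per arm, equal true rates, two-sided 95% Newcombe interval, 80% probability). At 27 per arm these are about 25 and 35. An attrition excess as large as the planned rate itself, 10 points, would be excluded only about one time in eight at 22 per arm.

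The figures cover per-patient yes/no outcomes, not the repeated questionnaires or vital signs. The opening of section 10 was not in the text available, so the absence of an Aim 3 rule is established for sections 5.2, 5.4 and 9.4. The point should be fixed, but it does not touch the sample, the conduct, the primary analysis or the monitoring board's review.

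**What to change.** - Section 5.2: delete the sentence on sufficiency for Aim 3. If a capability is to be stated, give the margin with its assumed rate, interval method and probability, for example about 28 points at a 10% rate and about 40 at 50% (22 per arm, two-sided 95% Newcombe, 80% probability), updated to the sample size finally stated in section 5.1.
- Sections 5.4 and 9.4: restate Hypothesis 3 and Aim 3 as estimation. Report adverse-effect, attrition and correct-guess rates by arm, with each difference and its 95% confidence interval.
- Section 9.4: state that a non-significant difference will not be reported as evidence that tDCS is no worse than sham.

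The cost is wording in three sections and a few confidence intervals. No patients are added. The price is a more modest statement about safety and feasibility.

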## 5.3 Primary Endpoint

**EFFECTIVENESS OF PAIRING TDCS WITH REHABILITATION.** *Hyp. 1:* Patients receiving tDCS with rehabilitation will achieve greater gains in strength and dexterity, with reduction in activity limitations and participation restrictions, than those getting rehabilitation alone. Responders/non-responders will be identified

Title: Improving Spinal Cord Injury Rehabilitation Interventions by Retraining the Brain

PI: [name]

Sub-site PI's: [name], [name], [name], [name], [name]

Protocol V 5.1 —2/3/2023

based on baseline clinico-demographic characteristics, such as the level of injury, degree of incompleteness and time post-injury, etc.

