## **9.4 Data Analysis Plan**

For aim 1, measures of function, strength/muscle power, dexterity, sensation, prehension, perception of independence in self-care, and quality of life will be collected, while for aim 2, metrics characterizing neurophysiology will be acquired and for aim 3, vital measurements will be noted daily.

Functional metrics adopted here are part of the National Institute of Neurological Disorders and Stroke (NINDS) Common Data Elements (CDEs), developed through the collaboration of the International Spinal Cord Society, the AIS, and the NINDS. The functional metrics span across all domains of the World Health Organization's (WHO's) International Classification of Function (ICF) model, including body function and structure, activity limitations, and participation restrictions. Metrics include Graded Redefined Assessment of Strength, Sensibility and Prehension (GRASSP), comprising the Upper Extremity Motor Score (UEMS) for strength, Nine-hole peg test (NHPT) for dexterity and sensation and prehension; Wolf Motor Function Test (WMFT) for measurement of functional abilities; Spinal Cord Independence Measure (SCIM) for evaluation of patient's ability to perform self-care; Canadian Occupational Performance Measure (COPM) to identify the patient's perceived level of daily participation in functional activities (e.g. cooking, cleaning, and hobbies). Each set of tests gives a different perspective of disability and testing all will allow us to get a full picture of patient function and quality of life before and after therapy. All measurements for aim 1 will take 120-150 min to complete. We will determine whether patients receiving tDCS in conjunction with rehabilitation experience greater recovery of function and independence than patients who receive rehabilitation alone (aim 1).

In aim 2, we will study the patient's neurophysiology, which will include the study of excitability of output pathways to a weaker muscle and a stronger muscle, and the cortical representations of these muscles. These measures of neurophysiology will be acquired using TMS and Hoffman or H-reflex. Neurophysiological tests will take 150-180 min to complete, which includes time allotted for breaks. We will test whether patients receiving tDCS in conjunction with rehabilitation experience greater gains in excitability of substrates devoted

Title: Improving Spinal Cord Injury Rehabilitation Interventions by Retraining the Brain

PI: [name]

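### GRASSP is named as the Aim 1 primary outcome, but the stated 80% power belongs to two component metrics, each tested alone, and no primary test or success rule is defined

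*Combined protocol and SAP*

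**What the plan says.** Section 5.3 (Primary Endpoint) names no instrument, score, time point or test. It gives Hypothesis 1: "Patients receiving tDCS with rehabilitation will achieve greater gains in strength and dexterity, with reduction in activity limitations and participation restrictions", compared with rehabilitation alone.

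The primary instrument appears only in section 5.2, which justifies sizing on muscle strength and NHPT because "both of these metrics are components of the primary outcome for Aim 1 (GRASSP"). Table 2 has no GRASSP row. Its two Aim 1 rows, each at α = 0.05, are:

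- strength, as a "between-group comparison of the numbers of weak (C6-T1) muscles that achieved clinically detectable improvements on MRC": effect size 0.938, 40 patients for 80% power;
- percentage change in NHPT: effect size 1.033, 32 patients for 80% power.

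The analysis text for Aim 1 in section 9.4 lists GRASSP, WMFT, SCIM and COPM and ends: "We will determine whether patients receiving tDCS in conjunction with rehabilitation experience greater recovery of function and independence than patients who receive rehabilitation alone". It gives no test, model, allocation of alpha or order of outcomes. On timing it says only that testing will "get a full picture of patient function and quality of life before and after therapy". Section 5.1 lists two pretests, a posttest and a 3-month follow-up without saying which pair defines the gain.

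On numbers, section 5.2 says: "Considering that there could be attrition of 10%, we expect to enroll 44 patients". Section 5.1 says: "At least forty-nine (up to 54) patients with chronic, incomplete", and then randomises 22 to each arm.

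**The concern.** A power statement describes a particular test. Here the named primary outcome (GRASSP), the powered quantities (a muscle count and an NHPT change) and the stated primary hypothesis (four domains) are three different things, and nothing in the analysis plan links them. A reader cannot tell which result would count as success for Aim 1.

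The error rates depend on the missing rule. If either powered component may carry the claim, the false-positive rate rises. If both must succeed, power falls below the stated level at 40 evaluable patients. If a GRASSP score is meant, no power has been stated for it. Section 3.5 presents this as the first efficacy trial of the combination, so the efficacy conclusion should rest on a rule fixed before results are seen.

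**Working it through.** **Inputs.** From section 5.2 and Table 2: effect sizes 0.938 and 1.033, α = 0.05, two-sample t statistics, two groups of 22, 10% attrition, and required totals of 40 and 32. Assumed, because the documents give no value: a correlation ρ between the two outcomes of 0 to 0.8.

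**1. Reproduce Table 2.** For n per arm, the t statistic has 2n − 2 degrees of freedom and noncentrality d√(n/2). The smallest total giving 80% power with a two-sided 0.05 test is 38 for d = 0.938 (stated: 40) and 32 for d = 1.033 (stated: 32). All 12 cells of Table 2 reproduce within 2 patients. A one-sided test would need only 30 and 26, so the table is two-sided. Its arithmetic is sound for separate tests.

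**2. Evaluable number.** 44 × 0.9 = 39.6, so 40 evaluable (20 per arm) matches section 5.2. The 22 + 22 randomised give at most 44 evaluable. If all 49 of section 5.1's minimum were randomised, 49 × 0.9 = 44.1, also about 44.

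**3. One pre-specified component.**

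| Measure | Noncentrality, 20 per arm | Power, 40 evaluable | Power, 44 evaluable |
|---|---|---|---|
| Muscle count | 0.938 × √10 = 2.97 | 82.4% | 86.0% |
| NHPT change | 1.033 × √10 = 3.27 | 88.9% | 91.7% |

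**4. Both components must succeed.** If independent, the powers multiply: 0.824 × 0.889 = 0.733 at 40 evaluable and 0.860 × 0.917 = 0.789 at 44. For correlated outcomes the joint power was simulated with pairs of t-tests.

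| ρ (assumed) | 40 evaluable | 44 evaluable |
|---|---|---|
| 0 | 73% | 79% |
| 0.3 | 75% | 80% |
| 0.5 | 76% | 81% |
| 0.8 | 79% | 84% |

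**5. Either component is enough, unadjusted.** If independent, the type I error is 1 − 0.95² = 9.75%. By simulation it is about 9% at ρ = 0.5 and 8% at ρ = 0.8. Counting only results in favour of tDCS, where a single two-sided 0.05 test has 2.5%, the independent case gives 1 − 0.975² = 4.9%, falling to about 4% at ρ = 0.8.

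**6. GRASSP as a single score.** The documents give no effect size, so its power cannot be computed. With 40 evaluable, 80% power needs a standardised effect of about 0.91. Assumed effects of 0.5, 0.6, 0.7 and 0.8 would give 34%, 46%, 58% and 69%. These show how far the answer depends on the missing figure and are not estimates for GRASSP.

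**The case against.** Several points on the other side are fair.

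- **Phase and aims.** This is a phase I/II trial of safety, feasibility, efficacy and mechanisms. A formal testing order for every efficacy outcome is one option, not an obligation. A defined primary measure is still needed where a powered efficacy comparison is claimed.
- **One instrument is named.** GRASSP is called primary, and SCIM and COPM are not individually called primary anywhere. This stands, but a name without a score, effect size or test does not say what will be compared.
- **The loss is modest for the two sized outcomes.** If both must succeed, power is 73–79% at 40 evaluable and about 79–84% at 44. This also stands.
- **Rules may exist elsewhere.** Section 10.1b mentions an interim analysis plan and mock tables that are not in the document, and some text next to the DSMB section was not available. What these contain is unknown. Section 9.4 is the analysis plan supplied, and it has no rule.

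A reader might infer that all four domains in section 5.3 must succeed, so that power is far below 80%, or that any one of four may count, so that the type I error is far above 5%. The documents support neither. Requiring all four would lower power further, but the plan does not adopt that rule and gives no effect sizes for SCIM or COPM.

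A reader might also take 49–54 enrolled and 22 + 22 randomised as a contradiction. The Subject Enrollment section counts a patient as enrolled once consent is given and eligibility is met, and randomisation follows a 3-week baseline phase, so the two can coexist. What does not fit is section 5.2's expectation of enrolling 44.

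**Conclusion.** The concern holds. The Table 2 figures are correct for what they describe, but they do not give the power of any defined Aim 1 test. The stated 80% is met only if one of the two sized components is pre-specified as the single primary test (82% or 89% at 40 evaluable). Requiring both gives 73–79%, and accepting either without adjustment gives a type I error of 8–10%, or 4–5% in favour of tDCS against 2.5%.

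All powers take the Table 2 effect sizes as true and use two-sided t-tests with equal arms; the ranges rest on assumed correlations of 0 to 0.8. The enrolment mismatch between sections 5.1 and 5.2 is a separate, smaller point. The documents do not show that anyone intends to choose the rule after seeing results, only that nothing prevents it. This should be fixed before unblinding.

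**What to change.** Make and date these changes before unblinding, through people without access to results by arm. Section 10.1b has statisticians sending the DSMB quarterly endpoint summaries, so that separation should be documented.

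1. **Name one Aim 1 primary measure** in sections 5.3 and 9.4, as change from pretest 2 to posttest, with a two-sample comparison at two-sided 0.05. Either define a GRASSP score and restate power from its own effect size, or use the muscle count that Table 2 powers, stating which limb is counted and that the pilot effect came from UEMS/MRC grades.
2. **Settle the other Hypothesis 1 outcomes.** Test dexterity, SCIM self-care and COPM in a fixed order at 0.05, stopping at the first non-significant result, or label them secondary with no confirmatory claim. If the chosen GRASSP score already contains dexterity, omit that step.
3. **Reconcile the numbers.** State consented, randomised and evaluable patients consistently in sections 5.1 and 5.2, and restate the power of the chosen primary at that evaluable number.

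The cost is an amendment with no new visits. A GRASSP score needs a new power calculation, which may show less than 80%. Choosing the muscle count changes the named primary mid-trial, so the amendment must be dated and justified. Outcomes late in the order may receive no confirmatory claim.
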